1.3. In-hospital cardiac arrest

Until recently, no validated risk models existed for predicting outcomes following in-hospital cardiac arrest. The National Cardiac Arrest Audit (NCAA), the national clinical audit of in-hospital cardiac arrest coordinated by ICNARC in collaboration with the Resuscitation Council (UK), was therefore established with a dataset including established important risk factors for outcomes following in-hospital cardiac arrest with a view to subsequent development of a risk model. In the previous research study, we developed and validated two novel risk models for in-hospital cardiac arrest. Based on over 14,000 in-hospital cardiac arrests in 122 hospitals, risk models were developed to predict both return of spontaneous circulation (ROSC) greater than 20 minutes and survival to hospital discharge. These models demonstrate good discrimination (c index 0.72 and 0.81, respectively) in external validation data and have enabled risk-adjusted comparisons among hospitals to be included, for the first time, in routine reporting for NCAA.

Simultaneous to our work developing risk models for NCAA, a risk model for predicting hospital mortality following in-hospital cardiac arrest was published from the United States Get With the Guidelines—Resuscitation registry. This identified largely similar risk factors to the NCAA risk models, but included additional predictors not available in the NCAA dataset, most notably preexisting comorbidities. Data linkage with HES will enable calculation of comorbidity indices from diagnoses and procedural codes recorded during the hospital episode, an approach that has recently been applied successfully in the UK Renal Registry. Combining this information with the existing risk factors will enable us to determine the contribution of chronic health conditions to outcome from in-hospital cardiac arrest with a view to either routinely linking data in the future, or establishing which comorbidity fields are important to collect directly within NCAA.

While many patients do not survive the initial resuscitation attempt, the treatment of those that do requires substantial resources and many patients will be admitted to a critical care unit. Data linkage between NCAA and the CMP will allow us to better understand patterns of critical care resource use and organ support following successful resuscitation and develop prediction models for likely resource use.

Little is known on longer-term outcomes following in-hospital cardiac arrest and data linkage to ONS will enable us to extend our risk models to predict longer term mortality.

Finally, data linkage with HES will enable us to estimate the cost of subsequent hospitalisations and its association with the measured risk factors.

2. Study aim and objectives

The aim of the proposed study is to better understand the epidemiology of, risk factors for and consequences of critical illness leading to improvements in the risk models used to underpin national clinical audits for adult general critical care, cardiothoracic critical care and in-hospital cardiac arrest using data linkage with other routinely collected data sources.

Specific objectives are:

- To improve risk models for adult general critical care by: (1a) developing risk models for
 mortality at fixed time-points and time-to event outcomes (by data linkage between the
 CMP and death registrations from ONS); developing risk models for longer term chronic
 health outcomes of (1b) diabetes (by data linkage between the CMP and the National
 Diabetes Audit) and (1c) end-stage renal disease (by data linkage between the CMP and the
 UK Renal Registry); and (1d) developing risk models for subsequent health care utilisation
 and costs (by data linkage between the CMP and HES)
- To improve risk models for cardiothoracic critical care by: (2a) enhancing risk factor data (by data linkage with the National Adult Cardiac Surgery Database); (2b) developing risk models for longer term mortality (by data linkage between the CMP and death registrations from ONS); and (2c) developing risk models for subsequent health care utilisation and costs (by data linkage between the CMP and HES)
- 3. To improve risk models for in-hospital cardiac arrest by: (3a) enhancing risk factor data (by data linkage between NCAA and HES); (3b) developing risk models for longer term mortality, health care utilisation and costs (by data linkage between NCAA and ONS); (3c) developing risk models for subsequent critical care utilisation (by data linkage between NCAA and CMP); and (3d) developing risk models for subsequent health care utilisation and costs (by data linkage between NCAA, ONS and HES)
- 4. Immediate translation of the improved risk models into practice through: (4a) adoption into routine comparative outcome reporting for the national clinical audits; and (4b) communication of research output to providers, managers, commissioners, policy makers and academics in critical care

3. Study design

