5.2.3. Risk models for in-hospital cardiac arrest (objective 3)

5.2.3.1. ROSC greater than 20 minutes and survival to hospital discharge (objective 3a)

Outcomes defined as ROSC greater than 20 minutes and survival to hospital discharge (hospital survival) from the existing NCAA data, the outcomes for the current risk models.

Patients included in the models will be all patients (aged 28 days or over) who received chest compressions and/or defibrillation following an in-hospital cardiac arrest and were attended by the hospital-based resuscitation team.

The starting point for the new risk models will be the previously developed risk models for each outcome.

New risk factors: pre-arrest risk factors obtained by data linkage with HES, the Charlson comorbidity index ^[28] and Elixhauser comorbidity measure ^[29] will be derived from International Classification of Disease (ICD-10) diagnostic codes and Office of Population Censuses and Surveys (OCPS) procedural codes, using methods employed recently by the UK Renal Registry ^[16], will be assessed for the optimal categorisation of the complex categorical risk factors.

5.2.3.2. Survival to 30 days, 90 days and 1 year and time to death (objective 3b)

Outcome defined as mortality at 30-days, 90-days and 1-year and days from cardiac arrest to death using the date of death obtained by data linkage with ONS.

Patients included in the models will be all patients (aged 28 days or over) who received chest compressions and/or defibrillation following an in-hospital cardiac arrest and were attended by the hospital-based resuscitation team.

The starting point for each new risk model will be the risk model for survival to hospital discharge developed in objective 3a.

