Aortic pathology – Root Segment Code 1

Aortic pathology – Ascending Segment Code 2

Aortic pathology – Arch Segment Code 3

Aortic pathology - Descending Aorta Segment Code 4

Aortic pathology – Abdominal Segment Code 5

Cardiopulmonary bypass

Intra-aortic balloon pump used (pre-operative)

Impeller device used (pre-operative)

Ventricular assist device used (pre-operative)

Other Support device used (pre-operative)

Intra-aortic balloon pump used (intra-operative)

Impeller device used (intra-operative)

Ventricular assist device used (intra-operative)

Other Support device used (intra-operative)

Intra-aortic balloon pump used (post-operative)

Impeller device used (post-operative)

Ventricular assist device used (post-operative)

Other Support device used (post-operative)

Cumulative bypass time

Cumulative cross clamp time

Total circulatory arrest time

Additive Euroscore

Logistic Euroscore

Hospital Episode Statistics – Admitted Patient Care data

Common key

Date of admission

Method of admission

Source of admission

Date of discharge

Destination on discharge

Method of discharge

Beginning of spell

Date episode ended
Date episode started
Duration of spell
End of spell
Episode duration
Episode order
Episode status
Episode type
All diagnosis codes
Primary diagnosis (4 characters)
All operative procedure codes
Main operative procedure code 3 character
Date of operations
Patient classification
Dominant procedure
Healthcare resource group: version 3.5
NHS-generated HRG code
NHS-generated HRG code version number
SUS generated core spell HRG
SUS generated HRG
SUS generated HRG version number
SUS generated spell ID
Code of GP practice
Record Identifier

HES-linked O	NS Morta	lity data
--------------	----------	-----------

Fact of Death

Date of Death

ICD 10th Revision Coded Cause(s) of Death

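### The protocol gives two timings for the comorbidity codes in the cardiac arrest models, and one of them lets post-arrest diagnoses into a predictor labelled pre-arrest

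*Protocol*

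**What the plan says.** Section 1.3 (background on in-hospital cardiac arrest) states: "Data linkage with HES will enable calculation of comorbidity indices from diagnoses and procedural codes recorded during the hospital episode". The stated aim is to "determine the contribution of chronic health conditions to outcome from in-hospital cardiac arrest", and then either to link data routinely or to choose comorbidity fields for NCAA to collect itself.

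Section 5.2.3.1 (objective 3a) introduces the same indices as "New risk factors: pre-arrest risk factors obtained by data linkage with HES", to be derived "using methods employed recently by the UK Renal Registry". The outcomes are ROSC greater than 20 minutes and survival to hospital discharge. No look-back window is given, nor any rule for codes from the stay in which the arrest happened. Appendix 2 adds no timing rule.

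The HES list in Appendix 1 asks for "All diagnosis codes" with episode and spell dates. It lists a date for operations but neither a date nor a present-on-admission marker for diagnoses. Section 5.2.3.2 takes the 3a survival model as the starting point for objective 3b.

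**The concern.** The episode that contains the arrest continues past it, to discharge or death, so the outcome decides how long a patient can go on collecting codes. Someone who dies at the arrest has little or no later care to be coded; a survivor may have a good deal. A comorbidity score built from that episode is therefore partly a consequence of the outcome it is meant to predict.

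Three things are at stake. First, the estimated contribution of chronic conditions, which is the stated purpose of the linkage, would be biased towards no harm. Second, that bias would feed the decision on which comorbidity fields to collect. Third, the 3b models start from the 3a model, and objective 4a puts the models into comparative reporting between hospitals. The validation in section 5.1.2 would not expose the problem if the predictor were built in the same way in the additional year of data.

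**Working it through.** The protocol states no figure for this point, so there is none to reproduce. The check is a reading of the text followed by an illustration of size.

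**Text**

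1. Section 1.3 places the codes within the hospital episode. Section 5.2.3.4 uses the original hospital episode, in contrast to subsequent ones, for the stay that includes the arrest.
2. Section 5.2.3.1 calls the variables pre-arrest. Both can be true only if codes entered after the arrest are removed.
3. Appendix 1 gives the date and time of the 2222 call (NCAA) and the start and end dates of each HES episode. Whole episodes can therefore be placed before or after the arrest, but diagnoses inside the episode that spans it cannot.
4. Where the protocol wants earlier records it says so: sections 5.2.1.2 and 5.2.1.3 refer to earlier years of audit or registry data. Section 5.2.3.1 has no equivalent.

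**Illustration 1: index points**

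- From section 3.2: survival s = 10,000/56,000 = 17.9%.
- Assumed: true points X ~ Poisson(1.5); logit P(survive) = α − 0.15X, so the true odds ratio is exp(−0.15) = 0.861 per point. Setting mean survival to 17.9% gives α = −1.31.
- Assumed: observed points = X + Poisson(a) in survivors and X + Poisson(d) in those who die. A logistic model is then fitted to observed points alone (large-sample limit).

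| a (survivors) | d (deaths) | Fitted odds ratio | c index |
|---|---|---|---|
| 0 | 0 | 0.861 | 0.548 |
| 0.1 | 0.1 | 0.869 | 0.547 |
| 0.3 | 0.3 | 0.884 | 0.544 |
| 0.12 | 0.1 | 0.881 | 0.542 |
| 0.15 | 0.1 | 0.900 | 0.535 |
| 0.2 | 0.1 | 0.931 | 0.524 |
| 0.3 | 0.2 | 0.935 | 0.524 |
| 0.3 | 0.1 | 0.992 | 0.503 |
| 0.6 | 0.1 | 1.176 | 0.558 |
| 1.0 | 0.1 | 1.421 | 0.631 |

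The fitted slope is zero when the mean observed score is equal in survivors and deaths. The true means, from E[X | survive] = Σ x·P(x)·P(survive | x)/s and its counterpart for deaths, are 1.325 and 1.538. The effect therefore vanishes when a − d = 1.538 − 1.325 = 0.213. With d = 0.1 that is a = 0.313, about three times the accrual in those who die. The excess is what matters, so the ratio changes with d.

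**Illustration 2: one yes/no condition**

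Assume 20% prevalence and a true odds ratio for survival of 0.50. With overall survival at 17.9%, survival is 0.1960 without the condition and 0.1087 with it. The cells are:

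- with the condition: alive 0.2 × 0.1087 = 0.0217; dead 0.1783
- without the condition: alive 0.8 × 0.1960 = 0.1568; dead 0.6432

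If 10% of survivors without the condition gain the code after the arrest, the alive cells become 0.0217 + 0.0157 = 0.0374 and 0.1412. The observed odds ratio is (0.0374 × 0.6432)/(0.1412 × 0.1783) = 0.96. At 5% and 20% it is 0.72 and 1.53. Adding 2% accrual in those who die gives 0.65, 0.87 and 1.40. At 40% prevalence with no accrual in deaths, the values are 0.60, 0.70 and 0.96.

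With no post-arrest codes, both illustrations return the assumed true odds ratio.

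**The case against.** The strongest reply is that the protocol never decides to use post-arrest codes. Section 1.3 is background and says only what linkage will make possible. The operative text is section 5.2.3.1, whose label states the right intent. Both sections rest the derivation on a registry method that cannot be checked from the protocol; if that method uses earlier admissions only, the problem disappears. The term hospital episode is not defined, and Appendix 1 separates episodes from spells. Section 5.1.4 says analysis plans will be finalised before modelling, and a look-back rule is ordinary content for such a plan. The dates needed to apply one are already requested.

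Most of this stands. It rules out the reading that the models will contain post-arrest diagnoses, and it shows that nothing irreversible has been fixed. It does not remove the conflict: the one explicit statement of source disagrees with the label in the specification, which goes beyond a detail left for later.

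The objection on size also stands. Accrual rates are assumed, each added code counts as a full index point, and no other predictor is in the illustration. A reader might infer from the lower rows of the first table that the effect will vanish or reverse. The documents do not support that, because they say nothing about accrual, and under mild differences the effect is only weakened.

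**Conclusion.** The point holds as an unreconciled conflict with a possible bias, at moderate severity and moderate confidence. If arrest-episode codes are used, the indices can include post-arrest diagnoses, and the requested fields cannot remove them within that episode. The bias makes comorbidity look less harmful when survivors gain more codes.

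Under the assumptions shown, a true odds ratio of 0.86 per point becomes about 0.88 to 0.93 when survivors gain 0.12 to 0.2 codes against 0.1 in deaths. It reaches 1 at roughly three times the accrual in deaths, at that same 0.1 rate. A reader might also infer that discrimination must be inflated. That does not follow: in the illustration the c index falls from 0.55 to 0.50 before rising to 0.63. An effect on hospitals' expected survival through coding depth is plausible, but nothing in the documents allows it to be sized.

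**What to change.** Reconcile sections 1.3 and 5.2.3.1 with one explicit rule:

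- The primary Charlson and Elixhauser terms use only HES episodes that ended before the arrest date. This covers earlier spells, and earlier completed episodes of the same spell.
- The look-back is the same length for every patient and is set by the HES extract period. NCAA data start on 1 April 2011 and the CMP linkage period on 1 April 2009. Two years would be available throughout if the HES extract also starts in April 2009, which the protocol does not state.
- An indicator for no prior admission enters the model.
- Codes from the arrest episode are used only in a sensitivity analysis.

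The rule should carry through to objective 3b. The cost is a short addition to the text and a date filter on fields already in Appendix 1. The downside is some under-recording of comorbidity in patients with no earlier admission; the indicator handles this in part, and the sensitivity analysis shows how much the choice matters.

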3.1. Design and theoretical/conceptual framework

Risk modelling study linking existing data from multiple sources

3.2. Sampling

The selection of sites is based on those participating in the CMP and NCAA.

The coverage of the CMP is extremely high, with 256 critical care units participating including over 97% of NHS adult general critical care units in England and Wales. We will link data for the period

1 April 2009 to 31 March 2015, enabling exploration of trends and fit of models over time, although only data from the last two years will be used to fit the final models as our previous research has established that the fit of risk models deteriorates over time. This will give a total sample size of over 850,000 admissions (700,000 critical care unit survivors) for exploring trends and fit over time with 330,000 admissions (280,000 critical care unit survivors) for model fitting. As the CMP is an ongoing programme, additional data will accrue while the development work is ongoing. At one year into the study, an additional 170,000 admissions (150,000 critical care unit survivors) will be available and the linkage will be updated providing data for external validation.

Of twenty-seven specialist cardiothoracic critical care units providing Level 3 (intensive) care, eight currently participate in the CMP. From 1 April 2009 to 31 March 2015 we will have a sample size of approximately 34,000 admissions to these units (3,000 deaths) for objective 2. The updated data linkage will include an additional 2,300 admissions (200 deaths) for external validation.

The coverage of NCAA is increasing and now stands at 181 hospitals, including over 75% of acute hospitals in England and Wales. From 1 April 2011 to 31 March 2015 we will have a sample size of approximately 56,000 in-hospital cardiac arrests (10,000 survivors) for objective 3. The updated data linkage will include an additional 16,000 in-hospital cardiac arrests (3,000 survivors) for external validation.

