5.1.2. Internal and external validation

Each newly developed or revised risk prediction model will be validated using the above measures both within the development sample and in independent validation data.

Where a prognostic model is based on a very large sample size and relevant variables are included in the final model, optimism is small and so, the apparent estimates of model performance (*c* index and Brier's score in the development data) are attractive because of their stability^[25]. However, to assess optimistic performance within the development data, the percentage of over-fitting will be estimated by the optimism-corrected statistics.

Where existing risk prediction models are modified, the performance of the revised model will be compared with the existing model using reclassification techniques. The improvement in reclassification will be quantified as the Net Reclassification Improvement NRI. We will calculate the NRI both using pre-defined categories of risk and also as a continuous measure (i.e. the proportion with any improvement in predicted risk compared against the proportion with any worsening in predicted risk).

After one year, the data linkage will be updated to provide an additional year of data to serve as independent validation data.

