5.2. Model specification

5.2.1. Risk models for adult general critical care (objective 1)

5.2.1.1. Mortality at 30-days, 90-days and 1-year and time to death (objective 1a)

Outcome defined as death (from any cause) within 30-days, 90-days or 1-year of admission to the critical care unit and number of days from admission to death, established by data linkage with death registrations from ONS.

Patients included in the models will be all those admitted to a critical care unit and discharged alive from the critical care unit.

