5.2.1.3. New diagnosis of end-stage renal disease post-critical care (objective 1c)

Outcome defined as recording of the patient in the UK Renal Registry database with a date of diagnosis of end-stage renal disease within one year following the date of discharge from hospital.

Patients included in the model will be all those discharged alive from acute hospital following a critical care unit admission, excluding any with a pre-existing diagnosis of end-stage renal disease as identified from data linkage with earlier years of data from the UK Renal Registry or by recording of an ongoing requirement for renal replacement therapy for irreversible end-stage renal disease in the CMP database

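### The single linkage update one year in leaves some or most validation patients without the full window that the 1-year outcomes need, and no outcome closing date is stated

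*Protocol*

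**What the plan says.** Protocol section 3.2 (Sampling) sets the admission period for objective 1 as "1 April 2009 to 31 March 2015, enabling exploration of trends and fit of models over time". It adds that "only data from the last two years will be used to fit the final models", which gives "330,000 admissions (280,000 critical care unit survivors) for model fitting". It then notes that "additional data will accrue while the development work is ongoing" and that "At one year into the study, an additional 170,000 admissions (150,000 critical care unit survivors) will be available and the linkage will be updated".

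Section 5.1.2 describes the same step: "After one year, the data linkage will be updated to provide an additional year of data to serve as independent validation data". It requires each newly developed or revised model to be validated both in the development sample and in those independent data. The synopsis gives a study period of 24 months.

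Several outcomes need long follow-up:

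- **1a (section 5.2.1.1):** "death (from any cause) within 30-days, 90-days or 1-year of admission to the critical care unit", plus time to death.
- **2b and 3b (sections 5.2.2.2 and 5.2.3.2):** mortality at 30 days, 90 days and 1 year; 3b adds time to death.
- **1c (section 5.2.1.3):** end-stage renal disease diagnosed "within one year following the date of discharge from hospital".
- **1b (section 5.2.1.2):** diabetes with a year of diagnosis in the calendar year following discharge.

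Section 5.1.4 assigns mortality at fixed time-points, including 1 year, to logistic regression. Time-to-event outcomes go to Weibull or Cox models.

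The protocol gives no calendar start date, no closing date for any outcome extract, no minimum follow-up rule and no second update. It does not say whether the update refreshes outcomes for patients already linked.

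**The concern.** Sections 3.2 and 5.1.2 fix the timing of the validation data by admission, not by outcome. A year of admissions collected during the first study year and linked at its end cannot all have a year of follow-up at that point. Logistic regression for 1-year death, and the performance measures in section 5.1.1 (c index, Brier score, calibration plot, Cox calibration regression, SMR), need a known status at one year.

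If patients with open windows were counted as event-free, observed events would be too few. A well-calibrated model would then appear to over-predict, with an SMR below 1. Objective 4a sends these models into routine comparative reporting, so a spurious calibration result would matter. The data come from external bodies under data-controller approvals (sections 4.1 and 6.2), so follow-up that was never extracted cannot be recovered by a later analysis decision.

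**Working it through.** **Inputs.** From section 3.2: 330,000 admissions in the two fitting years and 170,000 in the update. From section 5.1.2: the update adds one year. Assumptions: the validation year is 1 April 2015 to 31 March 2016 (the year after the stated window), admissions are uniform over time, and the outcome closing date is varied because none is given.

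**1. Is the update one year of intake?** 330,000 / 2 = 165,000 a year, against 170,000 stated. Yes, within rounding.

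**2. Share of the validation year with a full 365 days.** Let L be the lag from the end of the admission year to the outcome closing date. The share is P(U + L ≥ 365), with U uniform on 0 to 365 days, which is about L/365. Counting calendar days:

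| Outcomes close | Lag | 30 days complete | 90 days complete | 365 days complete |
|---|---|---|---|---|
| 31 Mar 2016 | 0 months | 91.8% | 75.4% | 0.3% (about 500 of 170,000) |
| 30 Jun 2016 | 3 months | 100% | 100% | 25.1% |
| 30 Sep 2016 | 6 months | 100% | 100% | 50.3% |
| 31 Dec 2016 | 9 months | 100% | 100% | 75.4% |
| 31 Mar 2017 | 12 months | 100% | 100% | 100% |

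Full completeness at the update itself would need the admission year to have ended 12 months earlier, at study start. No validation admissions would then accrue during the study, contrary to section 3.2.

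**3. Diabetes (1b).** With discharge date approximated by admission date, April to December 2015 discharges need audit data to 31 December 2016. January to March 2016 discharges need data to 31 December 2017. The share of the validation year with a closed window is 0% at 31 March 2016 and 75.1% at 31 December 2016 or 31 March 2017.

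**4. Effect if open windows are counted as event-free (1a).** Assume 20% 1-year mortality and F(t) = 1 − exp[−λ(t/365)^k], with λ = −ln 0.8 = 0.223 and k from 0.4 to 1.0. Neither assumption comes from the protocol. Observed/true = mean of F(min(U + L, 365)) / F(365):

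| Lag | k = 1.0 | k = 0.4 |
|---|---|---|
| 0 months | 0.52 | 0.73 |
| 3 months | 0.73 | 0.87 |
| 6 months | 0.88 | 0.95 |

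A perfectly calibrated model would show these values as its SMR.

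**5. The same for 3b.** Section 3.2 gives 10,000 survivors of 56,000 arrests, so 46,000 (82%) do not survive. Assume those deaths are early and all seen, that 10% to 30% of survivors die within the year, and that half of those later deaths are seen. In thousands, observed/true = (46 + 0.5)/(46 + 1) = 46.5/47 = 0.99, and (46 + 1.5)/(46 + 3) = 47.5/49 = 0.97.

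**6. Fitting sample (1 April 2013 to 31 March 2015), 1-year mortality.**

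| Outcomes close | 365 days complete | Incomplete of 330,000 |
|---|---|---|
| 31 Mar 2015 | 50.0% | 165,000 |
| 30 Jun 2015 | 62.5% | about 124,000 |
| 30 Sep 2015 | 75.1% | about 82,000 |
| 31 Dec 2015 | 87.7% | about 41,000 |
| 31 Mar 2016 | 100% | 0 |

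For 1b in the fitting sample, the share with a closed window is 37.7% at 31 March 2015 and 87.7% at 31 March 2016.

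**The case against.** The strongest reply is that the protocol describes admission windows and leaves outcome cut-offs to the analysis plan. Section 5.1.4 says plans will be finalised before modelling and lists survival, interval-censoring and illness-death methods. HES and ONS data arrive as separate extracts (section 4.1). The 1b exclusion for practices not submitting audit data in the subsequent year shows that later follow-up was considered. A later death extract within the 24 months is not ruled out.

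Much of this stands, and it rules out three stronger readings.

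- **A reader might infer that half the fitting sample lacks a year.** That follows only if outcomes also close on 31 March 2015. Section 3.2 counts admissions and does not say so. Outcomes to 31 March 2016 would remove the gap for 1-year mortality.
- **A reader might infer that the 1-year models cannot be validated at all.** The protocol leaves the start date and extract lag open, some patients may have a full year at the update, and a later extract could supply the rest.
- **A reader might infer that incomplete patients will be scored as event-free.** The protocol does not say this; it only lacks a rule against it.

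Nor does the size found for 1a carry over to every model. For 3b most deaths are early, and 2b also includes all admissions, so its early deaths are counted.

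The reply does not remove the conflict in the protocol itself. Section 5.1.2 requires every model to be validated on admissions that accrue during the study, and it plans one update. An analysis plan can choose censoring methods, but it cannot supply follow-up that was not extracted.

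**Conclusion.** The concern holds for validation of the 1-year binary outcomes: death in 1a, 2b and 3b, end-stage renal disease in 1c and diabetes in 1b. Under any timing consistent with section 3.2, some validation patients lack a full window at the planned update. With a lag of six months or less, that is about half of them or more.

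The bias is conditional on incomplete patients being counted as event-free. It would then be material for 1a (observed/true about 0.5 to 0.95, under the assumed 20% mortality and Weibull timing) and small for 3b (about 0.97 to 0.99, under the assumptions shown).

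Hospital-discharge outcomes are largely unaffected, as are 30- and 90-day outcomes given about three months' lag. Time-to-event models can censor. For the fitting sample the finding is only that no outcome closing date is given; the exposure for 1-year mortality ranges from none to 165,000 of 330,000.

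**What to change.** 1. State the outcome closing date for each source (ONS, HES, UK Renal Registry, National Diabetes Audit).
2. State that the year-one update refreshes outcomes for the original cohort as well as adding new admissions.
3. Admit a patient to fitting or validation for an outcome only if that outcome's full window closed before the source's extract date.
4. For 1-year outcomes, choose one of the following:
   - take a later outcome extract for the 2015/16 admissions;
   - use censoring-adjusted validation measures;
   - validate on the latest admissions with closed windows and fit on the two years before them.

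Under the last option the window must be set separately for each outcome. For 1-year mortality it is 2014/15 admissions if outcomes run to 31 March 2016, with fitting on 2012/13 and 2013/14. For 1c the year is counted from hospital discharge, so some late admissions drop out. For 1b, only discharges whose following calendar year is fully covered by the audit extract qualify; a January to March 2015 discharge needs data to December 2016.

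Keep the 2015/16 admissions for hospital-discharge, 30-day and 90-day outcomes.

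**Cost.** Mostly wording, plus an outcome refresh at a linkage already planned. A later extract would add a further data request; for 1-year mortality in all 2015/16 admissions it must run to 31 March 2017, and for 1b to 31 December 2017. Without a later extract or censoring-adjusted validation, the 1-year models rest on data about one year older. That is a real drawback, because section 3.2 notes that model fit worsens over time.
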